#### **4.2 Immunogenicity Assessment**

To assess humoral immunity, Anti-S1(including RBD) IgG antibodies will be measured by ELISA in a subgroup of volunteers in Babol and Sari (C1) and Zanjan (C2) before the first dose and 28 days after the last dose. In addition, on Days 5 and 28, an extra antibody measurement will be done on a random subset of 900 volunteers in Babol and Sari (30% of volunteers in these cities). Limiting these extra measurements in two cities is to minimize the blood sampling and ease the logistic issues. Neutralizing antibodies will be measured by the Virus Neutralization test (VNT) in a proposition of participants (100 individuals).

To assess Cell-Mediated Immunity (CMI), Interferon Gamma Release Assay (IGRA) will be performed on at least 130 participants from Babol or Sari.

#### **4.3 Safety Assessment**

Whether solicited or unsolicited, the local and systemic adverse events (AEs) will be recorded in diary forms by the volunteers. The AEs will be recorded from the first dose (Day 0) until five months after the last dose in both cohorts.

#### **4.3.1 Adverse Events (AEs)**

The AE is defined as any untoward medical events in participants that are temporally associated with the use of study interventions, whether or not considered related to vaccine/placebo. An AE can vary from clinical manifestations to abnormal test results.

After each injection, systemic and local pre-defined AEs will be registered using an online platform within three days. Solicited local AEs occur in the injection site and include pain, redness, swelling, induration, and warmth. Solicited systemic AEs are fever, chills, nausea, vomiting, malaise, fatigue, headache, diarrhea, pain in extremities, and rashes. Participants will record all these events using an online platform within three days after receiving each dose of vaccine or placebo. If any volunteer will not complete the diary, an active follow-up will be done on day four. Moreover, other unspecified symptoms (unsolicited AEs) will be followed up 28 days after each injection.

Serious Adverse Events (SAEs) are defined as any event which leads to a dangerous situation, hospitalization, longer duration of hospital stays, serious/permanent disability, congenital anomalies, requires a medical or surgical intervention to prevent permanent injury, or culminates in death. These events will be monitored up to five months after the last dosage of vaccine/placebo.

Medically Attended AEs (MAAEs) are adverse events after taking intervention that requires presentation to a health care provider, such as a general practitioner or emergency room visit for physical examinations. These events will be monitored up to five months after the last dosage of vaccine/placebo.

For monitoring and managing of AEs, the following measures will be performed:

- Active monitoring of participants for adverse events for half an hour after receiving each dose at vaccination sites.
- An Emergency medical services (EMS) ambulance will stand with three paramedics. There is an attending emergency medicine specialist with all first-aid and resuscitation equipment in place

All arrangements and coordination have been made with a supporting hospital in each city to transfer and visit participants who might suffer SAEs. In case of any SAE, the emergency specialists of the study will coordinate with the hospital an appointment for participants. We will provide 24-hour free-of-charge medical services in these hospitals for participants during the study.

- The solicited AEs (local and systemic) are recorded in online diary forms up to 72 hours after receiving each dose by volunteers. If any volunteer does not complete the diary, an active follow-up will be done on day fourth. During this period, medical services and consultations, and hospitalization are provided to volunteers who are affected by AEs.
- Passive monitoring of unsolicited AEs from the first day until day 28th is done through spontaneous reporting by participants to call centers or go to specified hospitals.
- SAEs and MAAEs are detected passively whenever a volunteer report to the call center or consults with the hospital. These participants will be followed actively until fully recovered.
- All SAEs and MAAEs should be reported at the earliest time possible (a few days) to the sponsor and PI, who will inform DSMB to decide about unmasking and withdrawing the participants from the study.
- In case of any SAE or fatal event that needs hospitalization, the CoPIs will report the case to the Pasteur Institute of Iran via an urgent phone call, which in turn reports to FDA, and the National Ethics Committee (NEC).

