### ***6.2.3 Safety population***

We will benefit from a “per-protocol (PP)” analysis to evaluate vaccine safety. In this approach, the solicited and unsolicited adverse events will be determined and compared between those subjects receiving at least one dose of vaccine and those receiving at least one dose of placebo.

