All volunteers will be instructed to coordinate with the call center and go to designated laboratories for a PCR test quickly within 48 hours in case of presenting with two or more of the following symptoms lasting for over 24 hours confirmed in positive PCR testing: Fever (temperature  $\geq 38^{\circ}\text{C}$ ), chills, new cough, sore throat, nasal congestion, fatigue, muscle or body pain, headache, nausea or vomiting, diarrhea, loss of smell or taste, or at least one respiratory sign or symptom (i.e., cough, O2 saturation  $< 91$ , shortness of breath, or clinical or radiographic evidence of pneumonia).

3) Nasopharyngeal and pharyngeal swabs will be taken from the symptomatic volunteer. If the volunteer cannot be present in the lab, the operator arranges a home visit/s for him/her to take samples and clinical assessment/s. If the home visit is impossible, the symptomatic volunteer is asked to make a pharyngeal gargle with a standard method and then bring it to the lab. If PCR turns to be negative yet the symptoms last for more than 2 days, the test will be repeated after 7 days. The volunteers with positive tests who do not need hospitalization will be visited by Phone daily until full recovery of symptoms. It is important

to take note that some manifestations of COVID-19 have overlapped with systemic AEs following immunization (e.g., myalgia, headache, fever and chills). Regarding that such AEs are more common within 3 days following vaccination in case of having other symptoms of COVID-19, an infectious disease specialist judges clinically and decides whether a sample for PCR is needed. All PCR-positive cases after the 2nd shot will be counted and included to estimate vaccine efficacy (primary outcome).

4) The volunteer must record all solicited local and systemic AEs within the first 72 hours post-vaccination in their online profiles. If any volunteer did not complete the diary, an active follow-up will be done on day four. Moreover, unsolicited adverse events will be followed up 28 days after each dose, and medically attended adverse events and serious adverse events will be monitored six months after the first dose.

5) All medical treatments and other vaccines received within the 28 days after each vaccine dose as well as AEs and SAEs will be recorded. All SAEs which need medical intervention will be recorded from screening day (Day 0) till the end of follow-up (6 months after the first dose).

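### COVID-19 endpoint events also count as SAEs and MAAEs, so overall SAE and MAAE totals by arm mix efficacy with safety and can mask a non-COVID excess in the vaccine arm

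*Protocol*

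**What the plan says.** Section 4.3.1 defines an AE as "any untoward medical events in participants that are temporally associated with the use of study interventions, whether or not considered related to vaccine/placebo". An SAE is "any event which leads to a dangerous situation, hospitalization, longer duration of hospital stays", with disability, congenital anomaly, intervention to prevent permanent injury and death also listed. For the third class, "Medically Attended AEs (MAAEs) are adverse events after taking intervention that requires presentation to a health care provider". For SAEs and MAAEs alike, "These events will be monitored up to five months after the last dosage of vaccine/placebo", which is month 6 in C1 and month 7 in C2. The window for other events is shorter: "other unspecified symptoms (unsolicited AEs) will be followed up 28 days after each injection". Solicited events are recorded for three days after each dose.

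On detection, "SAEs and MAAEs are detected passively whenever a volunteer report to the call center or consults with the hospital". The notes to Tables 1 and 2 send participants with COVID-19 symptoms to the same call center.

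Section 4.1.1 and the secondary outcomes table make hospitalization or death from COVID-19 part of the severe-disease endpoint. The safety row of that table asks for event frequencies by intensity and seriousness, from day 0 to five months after the last dose. Section 6.3 describes event frequencies in each arm with 95% confidence intervals, with serious and unsolicited events broken down by MedDRA body system. Section 6.2.3 says that solicited and unsolicited events are "compared between those subjects receiving at least one dose of vaccine and those receiving at least one dose of placebo".

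Table 1, note 3, acknowledges that "some manifestations of COVID-19 have overlapped with systemic AEs following immunization", but uses this only to decide whether a PCR sample is needed soon after a dose. No section says whether COVID-19 episodes are counted within the AE, MAAE and SAE figures or shown apart from them.

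**The concern.** Applied as written, the definitions put the same event on both sides of the benefit-risk account. A COVID-19 hospitalization is a severe-disease endpoint and an SAE. A COVID-19 case seen by a physician is a symptomatic-disease endpoint and an MAAE. If the vaccine works, the placebo arm has more of both, so the SAE and MAAE totals lean towards the vaccine by an amount set by efficacy and incidence. A moderate excess of non-COVID harm in the vaccine arm could then appear as a neutral or favourable total.

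**Working it through.** **Inputs from the protocol.** Section 6.1: placebo incidence 0.0055 per month; efficacy 50% (C1) and 70% (C2); arms of 14,400 and 3,600 (C1) and 4,800 and 1,200 (C2). Section 4.3.1: SAE and MAAE follow-up to five months after the last dose, so 6 months (C1) and 7 months (C2) from day 0. Section 4.1: efficacy counted from 14 days after the last dose. With 28 days taken as one month and 14 days as half a month, protection starts at 1.5 months (C1) and 2.5 months (C2).

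**The plan's own figure.** No safety figure is given, so the check is that these rates are the ones behind the sample size. For the two-sample exponential test with 4:1 allocation:

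N = {1.96·√[V(λ̄)(1/0.8 + 1/0.2)] + 1.2816·√[V(λv)/0.8 + V(λp)/0.2]}² / (λp − λv)²

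Here λ̄ = 0.8λv + 0.2λp, V(λ) = λ²/E(λ), E(λ) = λ/(λ+g)·[1 − exp(−(λ+g)T)] and g = −ln(1−d)/T. C1 (T = 2, d = 0.1) gives 17,971 against about 18,000. C2 (T = 3, d = 0.2) gives 5,370, and 5,946 on the log-hazard scale, against 6,000. The inputs are therefore the plan's. Section 6.1 also quotes cumulative incidences of 0.012 over two months and 0.018 over three, which imply about 0.0060 per month. Using that rate would widen the gaps below by about 0.0060/0.0055 = 1.09.

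**COVID-19 risk over the SAE/MAAE window.** Placebo: 1 − exp(−0.0055·m). Vaccine: 1 − exp(−0.0055·[s + (1−VE)(m−s)]), with s the start of protection.

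- C1 placebo: 1 − exp(−0.0055·6) = 3.25%. C1 vaccine: 1 − exp(−0.0055·[1.5 + 0.5·4.5]) = 1 − exp(−0.020625) = 2.04%. Gap 1.2 points.
- C2 placebo: 1 − exp(−0.0055·7) = 3.78%. C2 vaccine: 1 − exp(−0.0055·[2.5 + 0.3·4.5]) = 1 − exp(−0.021175) = 2.10%. Gap 1.7 points.

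**MAAE ratio with no vaccine harm.** Assumptions not in the documents: background MAAE risk b = 5% in both arms; a share f = 25-100% of cases attended. Ratio = (b + f·vaccine risk)/(b + f·placebo risk).

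| | f = 25% | f = 100% |
|---|---|---|
| C1 | 0.0551/0.0581 = 0.95 | 0.0704/0.0825 = 0.85 |
| C2 | 0.0552/0.0594 = 0.93 | 0.0710/0.0878 = 0.81 |

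The vaccine-arm MAAE excess that would be cancelled exactly is f times the gap: 0.3-1.2 points (C1) and 0.4-1.7 points (C2).

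**SAEs.** Assumptions not in the documents: 5-20% of cases are SAEs; non-COVID SAE risk on placebo 0.5-2%. With no vaccine harm, the ratio of totals reads 0.79-0.97 (C1) and 0.73-0.96 (C2). A true non-COVID ratio of 1.5 reads 1.01-1.43 (C1) and 0.93-1.42 (C2). A middle case in C1 has a 1% background and 10% of cases serious: (0.015 + 0.00204)/(0.010 + 0.00325) = 1.29. A two-sided 5% comparison of 14,400 with 3,600 would have 64% power for the non-COVID counts and 35% for the totals. This is illustrative, because the protocol specifies no safety test.

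**Short windows.** Three days is about 0.1 month, so the solicited gap is at most 0.0055·0.1·0.5 ≈ 0.3 per 1,000 per dose (C1) or 0.0055·0.1·0.7 ≈ 0.4 (C2). For unsolicited events over 28 days per dose, only the last half month falls under protection: 0.0055·0.5·0.5 ≈ 1.4 per 1,000 (C1) and 0.0055·0.5·0.7 ≈ 1.9 (C2). If protection began on day 0, these would be about 5 and 11 per 1,000.

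**The case against.** A reader might infer that the whole safety comparison is biased towards the vaccine. The protocol does not support that. The between-arm comparison in section 6.2.3 names solicited and unsolicited events only, and on the section 4.3.1 windows the effect there is nil to small. Section 4.3 does also speak of recording solicited and unsolicited AEs to five months after the last dose. On that reading unsolicited events would be more exposed, so the limit depends on the 28-day rule.

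A reader might also apply full efficacy from day 0. That gives 3.25% against 1.64% (C1) and 3.78% against 1.15% (C2), gaps of 1.6 and 2.6 points. It overstates the effect if protection starts only when the efficacy count does.

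The safeguards have weight. Section 4.3.2 classifies every SAE and MAAE for causality, with a coincidental class. Tables by body system would keep visible an excess in a system that COVID-19 does not touch. Neither removes COVID-19 from the totals, and section 4.1.1 lists manifestations that cross systems, from gastrointestinal symptoms to septic shock and multiple organ dysfunction.

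The attended share and background risks are assumptions. A share of 100% is probably high, since non-hospitalized cases are followed by phone. Dropout, and unmasking with access to national vaccination (section 3.3), would narrow the gap.

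Finally, tabulation may be settled in an SAP that is not shown, and the definitions are not wrong in themselves. What stands is that the protocol fixes definitions and arm-wise frequencies which, taken literally, place endpoint events in the safety totals.

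**Conclusion.** The point holds for overall SAE and MAAE totals, not for the safety comparison as a whole. The direction needs only a vaccine that works. At the plan's incidence and efficacy, with protection from 14 days after the last dose, the COVID-19 contribution differs between arms by up to about 1.2 points (C1) and 1.7 points (C2), scaled by the share of cases that are attended or serious. The resulting ratios rest on the assumed shares and background risks. Across those ranges the distortion runs from slight to enough to cancel a true SAE ratio of 1.5. This does not affect the efficacy analysis. It is worth correcting because these totals are an obvious summary of serious harm.

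**What to change.** In sections 6.2.3 and 6.3:

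- State that PCR-confirmed COVID-19 episodes meet the AE definition and, where the criteria apply, the MAAE and SAE definitions.
- Present SAE and MAAE totals by arm twice, including and excluding those episodes.
- Tabulate the COVID-19 episodes separately by arm and seriousness.

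Both totals should stand side by side. Making the COVID-excluded table the main one would condition on a post-randomisation event that the vaccine affects. It could also move any vaccine-enhanced disease, a subject Annexe 3 touches on, out of the main contrast; the separate table keeps it visible. Expedited and DSMB reporting are unchanged.

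The cost is one extra set of tables and a written rule linking events to PCR-confirmed episodes, which needs some judgement for complications. The PCR results and event records are already collected.

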#### **4.3.2 Causality Assessment of AEs**

All SAEs and MAAEs will be assessed and classified by the Adverse Events Classification Committee. We will use WHO's adverse event following immunization (AEFI) causality assessment methodology for a causality assessment of AE after injection. In this method, the cause-specific definitions provide clarity on "A. Consistent causal association to immunization" and "C. Inconsistent causal association to immunization (coincidental)." The association is considered "B. indeterminate" when adequate information on the AEFI is available, but it is not possible to assign it to either of the above categories. Moreover, cases without adequate information for causality conclusions are categorized as "D. unclassifiable."

## **5. Vaccination sites**

We will perform the trial in vaccination sites designed and equipped by local medical Universities in 8 recruited cities (Bandar Abbas, Kerman, Yazd, Isfahan, Babol, Sari, Zanzan, and Hamadan). All vaccination sites must include the following spaces:

- A hall for instruction and signing informed consent by volunteers
- A waiting hall for volunteers

- Medical examination and screening rooms
- Blood sampling units
- Vaccinations rooms
- Post-vaccination active monitoring hall
- Emergency and Cardiopulmonary Resuscitation (CPR) unit
- An ambulance (EMS), three paramedics, and at least an emergency medicine specialist will be ready at vaccination sites to provide primary care in case of serious adverse events.
- In each city, a supporting hospital will service volunteers for probable serious adverse events (SAEs).

Recruited laboratories will test the participants for PCR, screening, and serology. The principal investigator will follow the standard operating procedure (SOP) to perform the laboratory process. Pasteur Institute of Iran will be responsible for quality control (QC) and quality assurance (QA) based on pre-defined protocols. We mentioned the address of the vaccination sites, contracting labs, and investigators of recruiting cities in Annex 2.

## **6. Statistical Methods**

### **6.1 Sample Size**

Separate power calculations were performed for the two cohorts. To demonstrate a clinically meaningful difference, we assumed 50% efficacy for two-dose regimens (C1) based on WHO criteria and hypothesized 70% efficacy for the three-dose regimen (C2) based on an independent Technical Support Committee (TSC) opinion that considered the immune response results observed in phases I and II trials of the 2 and 3 dose regimens. Other assumptions included an exponential distribution, minimum baseline incidence of disease in two (0.012) and three-month (0.018) follow-ups (incidence rate: 0.0055 per month), maximum dropout proportion of 10% and 20%, and a vaccine-to-placebo ratio of 4:1. Type I (a two-sided hypothesis) and type II errors of 0.05 and 0.1 were considered for sample size calculation in each cohort. The total sample size was calculated to be about 18,000 participants in C1 (14,400 in the vaccine and 3,600 in the placebo group) and 6,000 participants in C2 (4,800 in the vaccine and 1,200 in the placebo group) using Stata software.

#### ***Software command for sample size calculation***

Software: Stata (v.14.2)

Cohort 1

power exponential 0.0055, hratio(0.5) power(0.9) nratio(4) fperiod(2) lossprob(0.1) losstime(2)

Cohort 2

power exponential 0.0055, hratio(0.3) power(0.9) nratio(4) fperiod(3) lossprob(0.2) losstime(3)

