**Outcomes**

**Primary Outcome**

Outcome	Definition	Measurement method	Timing of measurement
Symptomatic COVID-19-19 infection	Identification of SARS-CoV-2 RNA (two viral gene targets) in the respiratory samples of suspected cases	Real-time PCR	
C1: From day 14th after the 2nd dose until the end of efficacy study time
 
C2: From day 14th after the 3rd dose until the end of efficacy study time

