**Table 2. Timing of activities in C2 (3-dose regimen)**

No. of visit	1	2	3	4		
Objective of visit	Screening Dose 1 Blood sampling from 2000 subjects of Zanjan city §	Dose 2	Dose 3	Blood sampling from 2000 subjects of Zanjan city §	End of monitoring efficacy	End of monitoring adverse events
Month	Month 1		Month 2	Month 3	Month 5	Month 7
Day	0	28	56	84		
Acceptable interval (open window period) 	0	+ 7	+ 7	+ 7		
Informed consent Complete eCRF (demographic info, concurrent treatments, history of underlying conditions, etc.)	•					
Blood sampling to assess the previous infection of COVID-19 (Antibody assay)	•					
Physical examination 	•	•	•			
Randomization	•					
Intervention						
Vaccine injection and active monitoring for 0.5 hours after the shot	•	•	•			
Evaluation of vaccine efficacy						
Monitoring of symptomatic COVID-19 (ex-program visit) 	•					
Blood sampling 	•			•		

Safety evaluation						
Handover of diary form to volunteers 	●	●	●			
Returning and review of Diary form 		●	●	●		
Recording adverse event	●					
Recording AEs which need medical intervention and those end up with study stop Recording those interventions (treatments) for AEs 	●					
Recording SAEs and their related treatments 	●					
Recording other treatments and vaccines during the study period 	●					

§ Two cities of Zanjan and Yazd follow the three-dose scheme. Just in Zanjan city, blood samples will be taken for serologic assays from 2000 volunteers on days 0 and 84.

- 1) Window period means an acceptable interval that a volunteer can come for visit or to receive the intervention
- 2) A comprehensive physical examination encompasses the measurement of vital signs, height and weight on day 0. Before every vaccine shot, the volunteer's arm is inspected for regional lymph nodes. Every significant physical finding must be reported as a side event that needs medical intervention. Vital signs will be assessed before vaccination on days 0, 28 and 56. Febrile subjects on day 0 (the 1st dose of vaccine) will be excluded (a temperature beyond 38oC is defined as fever). Those volunteers having fever on days 28 and 56 (the 2nd dose of vaccine) reschedule for an alternative date (within the window period) to get their 2nd and 3rd shots.

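### The C2 sample-size calculation leaves out the roughly 70 days before cases count and any loss in that time; if efficacy monitoring ends at Month 5, power at N=6,000 is about 85-89% rather than the stated 90%, while a six-month end essentially preserves the claim.

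*Protocol*

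**What the plan says.** Section 6.1 assumes 70% efficacy in C2, a placebo "incidence rate: 0.0055 per month", 4:1 allocation and a "maximum dropout proportion of 10% and 20" per cent (the second figure is for C2). On error rates it states: "Type I (a two-sided hypothesis) and type II errors of 0.05 and 0.1 were considered". The result is about 6,000 participants, 4,800 on vaccine and 1,200 on placebo. The C2 command is "power exponential 0.0055, hratio(0.3) power(0.9) nratio(4) fperiod(3) lossprob(0.2) losstime(3"). It contains a follow-up of three months and a 20% loss by month three, and no term for a delayed start.

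The counting window is set elsewhere:

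- Start: the C2 scheme in section 3 puts dose 3 on day 56. Section 4.1 counts cases from 14 days after the second/third dose, and the Primary Outcome table gives, for C2, "From day 14 th after the 3 rd dose until the end of efficacy study time". That is day 70.
- End, first version: the column "End of monitoring efficacy" in Table 2 stands at Month 5.
- End, second version: section 6.2.5 estimates C2 efficacy follow-up at six months, four of them after dose 3.
- A different start: note 3 to Table 2 counts every PCR-positive case after the second shot towards the primary outcome.

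**The concern.** A sizing calculation should describe the exposure in which primary events can occur. Here, 6,000 is the number randomised, but the three months at risk do not begin at randomisation. Between day 0 and day 70 participants can be lost, or infected and so no longer able to supply a first countable case. If Table 2 governs, the window that remains is also shorter than three months.

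C2 is the only test of the three-dose regimen, and its placebo arm has 1,200 people, so the printed inputs yield fewer than 40 expected events. A loss of several events moves the power noticeably. If the stated type II error of 0.1 is not delivered, the protocol overstates the chance that C2 answers its primary question.

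**Working it through.** **Inputs (section 6.1).** Placebo hazard h1 = 0.0055 per month; hazard ratio 0.3, so h2 = 0.00165; weights 0.2 and 0.8, so pooled hazard hb = 0.2 × 0.0055 + 0.8 × 0.00165 = 0.00242; two-sided alpha 0.05; N = 6,000. Printed loss rate g = -ln(0.8)/3 = 0.0744 per month.

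**Formulas.** With lead-in L and window T (months), the probability of a countable event at hazard h is

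p(h) = exp(-(g+h)L) × h/(h+g) × (1 - exp(-(h+g)T)).

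Hazard-difference test: V0 = hb²/p(hb) / (0.2 × 0.8); V1 = h1²/(0.2 p(h1)) + h2²/(0.8 p(h2)); power = Φ[((h1-h2)√N - 1.96√V0)/√V1]. The log-hazard version replaces h²/p by 1/p and the difference by |ln 0.3|.

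**Plan's own figure (L = 0, T = 3).** p(h1) = 0.01467, p(h2) = 0.00443, p(hb) = 0.00648. Expected events: 1,200 × 0.01467 = 17.6 plus 4,800 × 0.00443 = 21.2, total 38.9. V0 = 0.00564, V1 = 0.01108. Power = Φ[(0.2982 - 0.1473)/0.1053] = Φ(1.43) = 92.4%. The N for 90% power is 5,370 by this formula and 5,946 by the log-hazard formula (power 90.3% at 6,000). For C1 the same formulas give 17,971 and 19,356 against 18,000 stated. The hazard-difference form thus matches C1 and the log-hazard form matches C2. The hazard-difference form is used as the main one because it is the milder for this point. Stata itself was not run.

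**Window under Table 2.** Start: 56 + 14 = day 70, so L = 70/30.44 = 2.30 months. End at Month 5:

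- five 28-day months (Table 2 sets day 84 at Month 3): day 140, T = 2.30;
- three calendar months after dose 3: about day 147, T = 2.54;
- five calendar months: about day 152, T = 2.70.

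**Power at N = 6,000, Month 5 end** (expected events; log-hazard power in brackets):

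| Loss assumption | T = 2.30 | T = 2.54 | T = 2.70 |
|---|---|---|---|
| 20% over five months, from randomisation (g = -ln(0.8)/5 = 0.0446) | 84.6%; 28.3 events [77.4%] | 87.2%; 31.1 [81.8%] | 88.7%; 32.9 [84.2%] |
| Printed rate, from randomisation | 81.6%; 25.6 [72.4%] | 84.3%; 28.0 [76.9%] | 85.8%; 29.6 [79.5%] |
| No loss before day 70, printed rate after | 86.8%; 30.6 [81.0%] | 89.1%; 33.5 [84.8%] | 90.4%; 35.4 [87.0%] |

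One cell in full (first row, T = 2.70): p(h1) = 0.01238, p(h2) = 0.00377, p(hb) = 0.00551; V0 = 0.00665, V1 = 0.01312; Φ[(0.2982 - 0.1598)/0.1146] = Φ(1.21) = 88.7%.

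In the first row expected events fall from 38.9 to 28.3-32.9, that is by 15-27%.

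**Six-month end (section 6.2.5), printed loss rate from randomisation.** Four 28-day months after dose 3 (day 168, T = 3.22): 89.8%. Four calendar months after dose 3 (about day 178, T = 3.54): 91.7%. Six calendar months (about day 183, T = 3.70): 92.5%. Log-hazard: 86.2%, 89.2%, 90.5%. With 20% loss spread over six months the hazard-difference values are 92.9-95.2%.

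**Start after dose 2 (Table 2 note 3), day 28 to day 140, printed loss rate from randomisation.** L = 0.92, T = 3.68: 43.3 events, 94.4%.

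**The case against.** The strongest objection is that the shortfall comes from another defect, the two C2 end dates. If section 6.2.5 governs, the delivered window is longer than the three months in the command and offsets the omitted lead-in, so leaving out a start lag is a harmless simplification. Most of this stands. The loss of power is conditional on Month 5. The omission in the command remains under either date, but matters little under the longer one.

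Second, Table 2 read whole would also bring in its note 3, which starts counting after dose 2 and gives about 94%. That is arithmetically right, but the note contradicts section 4.1 and the Primary Outcome table, so it cannot be relied on to rescue the power until the conflict is settled.

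Third, section 6.1 calls 20% a maximum. Running the printed rate from day 0 to day 140-152 implies 1 - exp(-0.0744 × 4.6) = 29% to 1 - exp(-0.0744 × 5) = 31% cumulative loss. This stands, and is why the first row of the table is the main result and 82-86% a sensitivity case.

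Fourth, section 6.1 also calls the incidence a minimum. Events scale almost in proportion to the hazard. In the first row the N for 90% power is 7,376 (T = 2.30) to 6,342 (T = 2.70), so 90% returns at about 0.0055 × 7,376/6,000 = 0.0068 down to 0.0055 × 6,342/6,000 = 0.0058 per month. A modestly higher attack rate would close the gap, but the stated power is a claim at the stated inputs.

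A reader might also infer that the command starts the clock at randomisation, leaving only about three weeks of countable time (91 - 70 = 21 days), or that it gives all 6,000 a full three months. The protocol supports neither: section 6.1 does not place time zero, and the loss term means that not everyone completes three months.

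**Conclusion.** The point holds in conditional form. The C2 command does not describe the exposure the endpoint delivers: it has no lead-in to day 70 and no loss before it. If efficacy monitoring ends at Month 5, power at N = 6,000 is about 85-89% under the protocol's own 20% maximum loss. The stated type II error of 0.1 is missed on almost every reading of Table 2; the one exception is the calendar-month window with no loss at all in the first 70 days, at 90.4%. If efficacy ends at six months, or four months after dose 3, power is about 90-92% by the hazard-difference formula at the printed loss rate, and the claim essentially holds.

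A flat statement that C2 power falls to 82%, or that C2 is too small, would go too far. It would ignore section 6.2.5 and take cumulative loss to about 30% against a stated 20% maximum.

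Assumptions: constant hazards, exponential loss, 30.44-day months for the hazard, doses given on the nominal days, and no countable first case in people infected before day 70. Using up the +7-day dose windows would shorten a window with a fixed end further. The choice of formula matters: the log-hazard form gives about 72-87% across the Table 2 readings.

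**What to change.** First reconcile section 6.2.5, the Primary Outcome table (with section 4.1), the Month 5 column of Table 2 and note 3 to Table 2, so that C2 case counting has one start and one end. Then redo the C2 calculation in section 6.1 for that window, with loss running from randomisation and a statement of the period that the 20% covers. Restate the power for N = 6,000, name the test formula used, and keep the 90% figure only if the chosen window delivers it.

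The cost is one recalculation and a rewording of section 6.1, plus the alignment of dates that the protocol needs in any case. N does not change. The downside is a less favourable stated power if Month 5 is kept.
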